
METHODOLOGY To include: -hypothesis - variables - methods -statistical analysis plan - power analysis
	
Hypothesis: Patients who receive a posterior capsular injection with Marcaine 0.5% during ACLR will report less pain and have less total narcotic use immediately post-op and up 4 days postoperatively compared to those that did not receive this injection.
 
Variables
 
 
1) Injection Group       
 
a. VAS Scores @ 15min/1 hour/POD1- 4
 
b. Time to first narcotic
 
c. Total narcotic use
 
d. 3 month Post-op visit assessment ((rule out chondrolysis)
 
 
 
2) Non-Injection Group       
 
a. VAS Scores @ 15min/1 hour/POD 1-4
 
b. Time to first narcotic
 
c. Total narcotic use
 
d. 3 month Post-op visit assessment (rule out chondrolysis)
 
 
 
 
Methods A prospective series of consecutive patients undergoing primary ACLR will be recruited from a preoperative log of patients seeing one of four sports medicine fellowship trained surgeons within our group. Patients undergoing primary unilateral anterior cruciate ligament reconstruction (ACLR) either with bone-patellar bone autograft or Achilles tendon allograft will be included by surgeons using similar techniques and fixation options.
 
Inclusion Criteria – Adult individuals (ages 18-60), both sexes, submitted to elective ACL reconstructions with or without partial menisectomies of the medial or lateral meniscus.
 
Exclusion Criteria – 1) Multiligamentous injury or revision surgery 2) Known narcotic/substance abuse or regular opiate use 3) Known allergy to any medication or anesthetic being used in this study 4) Patients with pre-existing diabetic or femoral neuropathy 5) INTRAOPERATIVELY- if chondral microfractures, inside-out or outside-in meniscal repairs were performed (***)Since these additional surgeries within the joint may increase the perceived level of pain post-op(***)
 
After consenting to participate, subjects will be randomized into one of two groups. Using a random number generator,

<http://stattrek.com/statistics/random-number-generator.aspx>

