60 consecutively enrolled patients will be placed in their appropriate study arm. (Odd numbers = Control Group) (Even numbers = Experimental Group). Only the patient will be blinded to which arm of the study they belong.

Group 1(Control) patients will undergo routine arthroscopically assisted ACLR surgery with a standardized postoperative protocol. Group 2 (Experimental) patients will undergo the same procedure with the same postoperative protocols as Group 1, with the addition of the posterior capsular injection of 20 cc of Marcaine 0.5%. There are no placebo treatments being offered and the surgeons and operating room staff are not blinded to the subjects group. Injecting marcaine in this study will be performed in accordance with its standard use according to the FDA labeling/guidelines. The physicians will use their discretion as to the appropriate location for the injection into the posterior capsule of the knee which should bring no additional risks than expected for a knee injection.

At the conclusion of the case, each patient will receive a dry sterile dressing, followed by a compressive wrap and a hinged knee brace locked in extension. No drains, pain pumps or nerve stimulators will be used. The nurses in the recovery room who will be administering the VAS assessment and recording time and frequency of pain medication dosing will be blinded to the patients' Group number. The nurses will provide pain medications and the visual analog assessment for their duties in the post-op anesthesia unit, and are not administering drugs or procedures specifically for research purposes.

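### Nothing keeps allocation concealed until the intraoperative exclusion check (criterion 5) is complete, so an operator who knows the arm could exclude patients after randomization

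*Protocol*

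**What the plan says.** All references are to the Protocol, METHODOLOGY section, unless noted.

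- **Recruitment (Methods).** Patients are "recruited from a preoperative log of patients seeing one of four sports medicine fellowship trained surgeons within our group".
- **Allocation (Methods).** "After consenting to participate, subjects will be randomized into one of two groups". A random number generator is used, odd numbers giving control and even numbers the injection, and "60 consecutively enrolled patients will be placed in their appropriate study arm". No other time point is given.
- **Inclusion Criteria.** Patients are eligible "with or without partial menisectomies of the medial or lateral meniscus".
- **Exclusion Criteria, item 5.** Patients are removed "INTRAOPERATIVELY- if chondral microfractures, inside-out or outside-in meniscal repairs were performed". The reason given is: "Since these additional surgeries within the joint may increase the perceived level of pain post-op".
- **Blinding (Methods).** "Only the patient will be blinded to which arm of the study they belong", and "the surgeons and operating room staff are not blinded to the subjects group". A later paragraph says that the recovery-room nurses who give the VAS and record pain medication are also blinded.
- **Approx Budget.** Envelopes for the randomization are costed. Who holds them and when they are opened is not stated.

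**The concern.** Criterion 5 is not a baseline characteristic. It depends on what is done in theatre: a partial meniscectomy keeps the patient in, while microfracture or either named type of meniscal repair takes the patient out. The person whose actions settle eligibility is the surgeon, who is unblinded.

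If the arm is known before that point, randomization no longer guarantees that the retained groups are comparable. Choosing or recording a procedure differently by arm, even without intent, would leave different mixes of patients. The Protocol itself links the excluded procedures to pain, so the VAS and narcotic comparisons could shift, in either direction. Blinding the patient and the recovery nurses gives no protection here, because the exclusion happens before any pain is assessed.

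The timing of disclosure is a trial procedure that must be settled before the first patient. It is not something a protocol normally leaves to its analysis plan.

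**Working it through.** **1. Order of events**

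| Step | What the Protocol fixes |
|---|---|
| Consent | Before randomization |
| Randomization | After consent; no latest time point |
| Disclosure of the arm to the surgeon | Not stated |
| Criterion 5 check | During surgery |
| Injection (Group 2) | Point in the operation not stated |

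Both of these sequences comply with the text:

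- consent → envelope opened → surgery → criterion 5 check → exclusion
- consent → surgery → criterion 5 check → envelope opened

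Only the second protects the comparison, and nothing requires it. The Protocol also does not say how a patient who is randomized and then meets criterion 5 is handled.

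**2. The plan's own figure**

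Inputs from Power Analysis: difference 2, SD 2.5, two-sided alpha 0.05, equal-variance t-test. By the noncentral t distribution, 25 per arm gives 79.1% power and 26 per arm gives 80.7%. The stated 26 per arm (52 in total) is reproduced and is not in question. The enrolment of 60 leaves a margin of 8, and 8/60 = 13.3%.

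**3. Illustrative size of the bias (all inputs assumed)**

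The Protocol gives no rate for criterion 5. Let p be the share of patients with the relevant pathology, all excluded in one arm. Let b be the share of all patients excluded for it in the other arm. Let D be their extra pain in VAS points. The second arm then retains (p − b) of these patients among (1 − b), so

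spurious difference = D × (p − b)/(1 − b)

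| p | b | D = 1 | D = 2 |
|---|---|---|---|
| any | equal to p | 0 | 0 |
| 10% | 5% | 0.05 | 0.11 |
| 20% | 10% | 0.11 | 0.22 |
| 20% | 5% | 0.16 | 0.32 |
| 20% | 0% | 0.20 | 0.40 |

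For example, 2 × 0.15/0.95 = 0.32. The last row is the extreme in which nobody is excluded in one arm. A shift of 0.40 with 26 per arm would raise the two-sided rejection rate under no true effect from 5% to about 8.7%.

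The Power Analysis does not name the outcome to which its difference of 2 belongs; it is read here as VAS points. On that reading, 0.32 is 0.32/2 = 16% of the planned difference.

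**4. Effect on numbers (assumed exclusion rate r)**

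| r | Left if all 60 are randomized before the check | Power | Consents needed to randomize 60 after it, 60/(1 − r) |
|---|---|---|---|
| 5% | 57 | 84.3% | 63.2 |
| 10% | 54 | 82.2% | 66.7 |
| 15% | 51 | 80.0% | 70.6 |
| 20% | 48 | 77.4% | 75.0 |

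If the 60 are randomized after the check, criterion 5 removes none of them, and 30 per arm gives 86.1% power before any other loss.

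**The case against.** The strongest reply is that the Protocol is silent on this point rather than wrong. Randomizing after consent remains true under the proposed fix, and budgeted envelopes are compatible with opening them late. With no placebo, whoever injects must learn the arm by then; the statement that surgeons are unblinded does not say that they know it before the arthroscopic findings. This stands: early disclosure is permitted by the text, not stated in it.

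The mechanism can also be called thin. Criterion 5 turns on whether named procedures were performed, so a surgeon would have to alter or misrecord an operation because of a planned local anaesthetic injection. Nothing in the Protocol suggests that. The illustration also does not fit every route. If knowing the arm led a surgeon to avoid a repair, the retained patient would not carry the pain of that repair. The formula fits where the procedure was done but the patient was kept, or where the underlying lesion itself brings more pain. These points stand as limits on likelihood and size.

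Finally, a later analysis plan could keep all randomized patients in their assigned arm. That would help only if outcome data are collected on those meeting criterion 5, which the Protocol does not provide for. It would not conceal an allocation that the surgeon already knew.

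**Conclusion.** The concern holds as a gap in the design. The Protocol sets the earliest time for allocation and omits the limit that matters, so following it as written allows exclusion after randomization, on grounds it links to pain, by an operator who may know the arm.

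No bias is shown, and its size cannot be derived from the documents. Under the assumed inputs it lies between 0 and 0.32 VAS points, or 0.40 in the extreme case. That is modest beside a planned difference of 2, and it is zero if exclusion is equal in the two arms. No stated figure is in error. The point should be fixed because the safeguard is simple and cannot be supplied after the trial has run.

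**What to change.** Keep consent before surgery. Add to Methods that the allocation envelope is opened only after the meniscal and chondral work is done and criterion 5 has been confirmed and recorded as not met, and before the injection would be given. Define the 60 as patients randomized at that point.

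Because the Protocol does not say when in the operation the injection is given, the investigators should confirm that their sequence allows this and write it down.

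The cost is one or two sentences and envelope handling in theatre. Consented patients who meet criterion 5 would not be randomized, so on average about 63, 67, 71 or 75 must consent at assumed rates of 5%, 10%, 15% or 20%. No extra randomized patients, staff or procedures are needed, and no treatment rule changes.

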
PROJECT TITLE
	
Pain outcomes after posterior capsular injection during Anterior Cruciate Ligament (ACL) reconstruction: A prospective, randomized trial.

BACKGROUND and RELEVANT REFERENCES
	
Post-operative pain control following elective anterior cruciate ligament reconstruction continues to be a hurdle for orthopaedic surgeons. This obstacle becomes particularly problematic during the first 36 hours after the operation, when the patient is experiencing pain at its peak intensity. Good control of pain leads to better patient comfort, confidence to place weight on the operative limb and improved ability to perform critical exercises in this period to improve joint range of motion. (Rev Bras Ortop. 2015 Jun 16;50(3):300-4)
 
A variety of anesthetic techniques have been employed to reduce pain including: cryotherapy, systemic analgesic and anti-inflammatory drugs, intrathecal, regional blockade of peripheral nerves and frequently intra-articular injections. Each technique has been studied at length with mixed but overall favorable results. However, in the authors' experience, after femoral nerve blockade, patients continue to complain of posterior knee pain in the Post-Anesthesia Care Unit (PACU) and peri-operative period. Intra-articular injections comprised of morphine and other Na-channel blocker analgesics may curb some of this pain by bathing the posterior capsule in anesthetic. However, there is still a large concern amongst orthopaedic surgeons about the potential harm these agents may have on the knee's healthy articular cartilage surfaces. The long term effects, including chondrolysis have been documented in the shoulder and while in the short term this effect is diminished there is still hesitation among surgeons to use this form of pain blockade.
 
This has led the authors to adapt a technique of isolated posterior capsular injections after total knee replacements from the joint arthroplasty literature, which has shown favorable results with low complication risk. (Orthop Clin North Am. 2015 Jan;46(1):1-8). We plan to study the effectiveness of this technique during ACL reconstruction in an attempt to curb the amount of posterior knee pain and decrease the overall narcotic use postoperatively while limiting the exposure of the native cartilage to harmful agents.
 
References: See Attached Sheet

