	
outcome during knee pain medication injection studies).
 
Statistical Analysis Based on previous studies, the Mann-Whitney U test will check differences between numeric variables. Nonparametric Kruskal-Wallis tests can compare the analgesia level in the two groups and if possible ANOVA test can compare the analgesia duration. Chi-square tests will be utilized for any potential complications which will also be recorded. (J Inj Violence Res. 2013 Jun; 5(2): 84-88.) (Acta Ortop Bras. 2012;20(5); 285-90)
 
Power Analysis Prelim Power Analysis per STATS department @ Cedars: sample sizes of 26 for each group (N1=N2=26) = Total 52 patients to achieve 80% power to reject the null hypothesis of equal means when the population mean difference is 2 with a standard deviation for both groups of 2.5 and with a significance level (alpha) of 0.050 using a two-sided two-sample equal-variance t-test. A total of 60 patients will be enrolled to ensure we achieve adequate power for the study.

CLINICAL RELEVANCE IMPACT
	
Despite the addition of selective regional blockade by the anesthesia team including femoral and saphenous nerve blocks, a portion of patients are still experiencing post-operative knee pain within the first few hours to days after the procedure. Pain may be a result of the femoral tunnel drilling which theoretically may be relieved by a posterior capsular injection. Eliminating this painful period will improve the patient’s subjective experience undergoing surgery, and may also allow for earlier range of motion and participation in rehabilitation strengthening exercises performed by the patient in the peri-operative period.

APPROX BUDGET Include comprehensive and detailed budget. Do NOT include any overhead expenses
	
Marcaine 0.5% with epi & 20 cc, syringe = Pending Paper VAS forms = Pending (< \$100) Envelopes for randomization process = Pending (\$<50) Statistician = Pending

AUTHORS indicate areas of involvement
	
1. _[name] – Primary Researcher  2. _[name] – Principle Investigator  3. _[name].  4. _[name]. 
 
1= idea development/project design; 2=data collection; 3=data analysis; 4=data interpretation; 5=manuscript preparation/revisions

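### Injection site is left to each of four surgeons with no stated record of it, and allocation is not balanced by surgeon: no bias, but a modest, cheaply avoided loss of precision and interpretability

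*Protocol*

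**What the plan says.** All places are in the Protocol.

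- **Intervention (Methodology, Methods).** The experimental arm has the control procedure "with the addition of the posterior capsular injection of 20 cc of Marcaine 0.5" (percent). Agent, concentration, volume and target structure are therefore the same for everyone. On the site within that structure: "The physicians will use their discretion as to the appropriate location for the injection into the posterior capsule of the knee". Nothing says that the site used is written down.
- **Surgeons (Methods).** Patients come from "one of four sports medicine fellowship trained surgeons within our group", and "will be included by surgeons using similar techniques and fixation options". That wording covers the reconstruction, not the injection.
- **Allocation (Methods).** "After consenting to participate, subjects will be randomized into one of two groups", by random number: "Odd numbers = Control Group) (Even numbers = Experimental Group". No blocks or strata are described. The budget lists envelopes for the randomization.
- **Blinding (Methods).** Surgeons and operating room staff know the arm.
- **Sample size (Power Analysis).** "sample sizes of 26 for each group (N1=N2=26) = Total 52 patients to achieve 80% power", for a mean difference of 2 with a standard deviation of 2.5. Sixty are to be enrolled.
- **Rationale (Background).** The technique is meant to reduce posterior knee pain "while limiting the exposure of the native cartilage to harmful agents".

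**The concern.** The injection is the only planned difference between the arms. The nerve block, postoperative protocol and pain medication around it are standardised, while its placement is left open and, as far as the protocol says, unrecorded. The rationale itself gives placement a role in both pain relief and cartilage exposure. If sites differ and some work less well, the average effect shrinks, and afterwards nobody could tell a weak injection from a varied one.

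Separately, four surgeons share 60 patients under an allocation that ignores surgeon. If pain differs by surgeon, chance differences in surgeon mix add noise that balanced allocation would remove. At stake are precision and the ability to interpret and repeat the result.

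**Working it through.** **Inputs from the protocol:** difference 2, SD 2.5, two-sided alpha 0.05, 26 per group, 60 enrolled, four surgeons, individual randomisation.

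**Assumptions, because the protocol gives no figures:** 15 patients per surgeon (or 30/15/10/5); a surgeon intraclass correlation (ICC) of 0 to 0.20; the difference of 2 is in VAS points; each number is drawn independently.

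**1. The plan's own figure.** Noncentrality = 2 / (2.5 × √(2/n)).
- n = 25: 2.828, power 0.791
- n = 26: 2.884, power 0.807
- n = 30: 3.098, power 0.861

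So 26 is the smallest group size that reaches 80%, and the stated figure reproduces.

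**2. How far the allocation can drift.**
- Arm sizes, Binomial(60, 0.5): the chance that the smaller arm falls below 26 is 0.245.
- One surgeon with 15 patients, split 10:5 or worse: 2 × 4944/32768 = 0.302. At least one of four: 1 − 0.698⁴ = 0.76.
- Split 11:4 or worse: 2 × 1941/32768 = 0.118. At least one of four: 1 − 0.882⁴ = 0.40.
- With volumes of 30/15/10/5, the chance of a 2:1 split or worse for some surgeon is 0.74.
- If the generator instead deals exactly 30 per arm, arm sizes cannot drift but the surgeon mix still can. One surgeon's 10:5 chance is then 2 × P(X ≤ 5) = 0.23, with X hypergeometric (15 drawn from 60, of which 30 experimental).

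These are chances of uneven splits. Step 3 shows what they do to the result.

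**3. Effect on the comparison.** Let τ = 2.5√ICC be the between-surgeon SD. Take 30 per arm and 15 patients per surgeon, a of them experimental. That surgeon's share differs between arms by (2a − 15)/30. Var(a) = 15 × 0.25 × 45/59 = 2.860, so the share difference has variance 4 × 2.860/900 = 0.0127. Over four surgeons the sum is 0.0508, and the chance shift in the treatment difference has SD τ√0.0508 = 0.225τ.

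The simulated columns come from 20,000 trials of 60 patients with independent 1:1 draws and an unadjusted t-test. Ranges cover the two volume patterns. The last column is the noncentral t at 30 per arm with SD 2.5√(1 − ICC).

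| ICC | τ | SD of shift (formula) | 95th percentile of absolute shift (simulated) | Power, simple and unadjusted (simulated) | Power, balanced and adjusted (approx.) |
|---|---|---|---|---|---|
| 0 | 0 | 0 | 0 | 0.853–0.855 | 0.861 |
| 0.02 | 0.354 | 0.080 | 0.15–0.17 | 0.858–0.859 | 0.868 |
| 0.05 | 0.559 | 0.126 | 0.25–0.26 | 0.860–0.862 | 0.878 |
| 0.10 | 0.791 | 0.178 | 0.35–0.38 | 0.864–0.869 | 0.895 |
| 0.20 | 1.118 | 0.252 | 0.49–0.53 | 0.870–0.881 | 0.926 |

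The mean shift is about 0 throughout, and type I error is 0.048 to 0.053. The gain from balancing and adjusting runs from 0.861 − 0.855 = 0.006 at ICC 0 to 0.926 − 0.870 = 0.056 at ICC 0.20, or about 1 to 6 points. Spending three degrees of freedom on surgeon lowers the last column by less than 0.001.

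**4. Dilution if sites differ in effect.** Suppose the four surgeons' injections have different effects with variance v, in equal shares. The spread arises only in the experimental arm, so the pooled SD is √(6.25 + v/2). At 30 per arm:

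| Assumed effects | Mean | v | Pooled SD | Power |
|---|---|---|---|---|
| 3 / 2.5 / 1.5 / 1 | 2 | 0.625 | 2.562 | 0.845 |
| 2 / 2 / 1 / 1 | 1.5 | 0.25 | 2.525 | 0.619 |
| 2 / 2 / 2 / 0 | 1.5 | 0.75 | 2.574 | 0.602 |
| 2 / 2 / 0 / 0 | 1 | 1 | 2.598 | 0.311 |

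Variation alone costs little. Power falls when the average effect falls. The protocol gives no basis for choosing among these rows, and without a record of the site neither would the trial data.

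**The case against.** A reader might infer that treatment is confounded with surgeon. The protocol does not support that. Patients are randomised individually, no surgeon is tied to an arm, and control patients receive no injection, so differences in injection cannot fall unequally between arms. Only chance imbalance in surgeon mix remains, and the test already allows for it.

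A reader might also infer that the experimental treatment is in fact several techniques, or that drug will enter the joint in differing amounts. The text permits different sites within the posterior capsule. It does not show that the surgeons use them, and it says nothing about amounts reaching the joint. The 76% chance of a lopsided split is correct under its assumption, but it is not a measure of harm to the result.

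The other points against are partly right:

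- A comparison of injection at the surgeon's chosen capsular site with no injection is a coherent pragmatic question. That stands, and it is a reason to record the site without restricting it.
- Power exceeds 80% in every row of the step 3 table without any change. That stands too, and it limits the weight of the point.
- Adjustment for surgeon may sit in a statistical analysis plan that is not shown. Its absence here is not counted as a fault; it is mentioned because the analysis should follow the blocking.
- Unblinded surgeons could guess some allocations from short block sequences, and exclusions made during surgery could leave blocks incomplete. Both are real but small, and the first can be limited.

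**Conclusion.** The point holds as a modest improvement to the design. The protocol does not say that the injection site is recorded, and it does not balance allocation across four surgeons. The treatment comparison stays unbiased with type I error near 0.05. The chance shift from surgeon mix is within about 0.5 VAS points in 95% of trials even at an ICC of 0.20, against a planned difference of 2. The avoidable loss is about 1 to 6 points of power at 30 per arm.

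The larger uncertainty is dilution. Power could stay near 0.85 or fall well below 0.80, depending on site effects that are assumed here, and the trial as written could not tell which had happened. ICC, surgeon volumes and site-specific effects are all assumptions, and the power figures are for a t-test, not for the Mann-Whitney test that the protocol also names.

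**What to change.** 1. Generate the random list in permuted blocks within surgeon, with block sizes that vary and are kept from the surgeons, and deliver it through the envelopes already budgeted, sealed.
2. Compare the arms within surgeon, for example with a surgeon-stratified Mann-Whitney (van Elteren) test or a surgeon term in the model. This may be placed in the analysis plan.
3. Add one line to the operative form recording the injection site used.

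Which site is right, and whether the surgeons should agree a common technique, are clinical decisions for them and are not prescribed here.

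**Cost:** four short lists instead of one, and one form line. No extra patients or staff. The downside is that blocked allocation is slightly more predictable to unblinded surgeons, which is why block sizes must vary and stay concealed.
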